5.5.1.1 Stopping Rules

In order for the DMC to make its recommendation for continuation of the study, it will be necessary for them to see the analyses for the primary outcome measure every time that the report is run and it is possible to calculate the primary outcome measure. Periodic monitoring of interim results can significantly affect the probability of making an incorrect decision. A number of formal techniques have been developed for interpreting interim results. At the organizational meeting, the DMC will select the technique that it wants to use to monitor the study. Suggested techniques are the Haybittle-Peto and Lan-DeMets group sequential boundaries. For the Haybittle-Peto method, a constant z-statistic is used as the monitoring boundary. The Lan-DeMets procedure produces decision boundaries that are quite conservative over the first several looks and then gradually converges to the nominal alpha levels as the final look is approached. The DMC will also analyze the safety data from the study to determine if the study should terminate. This will continue throughout the study.

5.5.2 Executive Committee

The Executive Committee is the management and decision-making body for the operational aspects of the study and will monitor the performance of participating medical centers and the quality of data collected. The Executive Committee will formulate publication plans and will oversee the publication and presentation of all data from the study. The Committee must grant permission before any study data may be used for presentation or publication. The Executive Committee is comprised of the Chairmen, PPCSP Biostatistician and Project Manager, LSIs and Subject Matter Experts.

6 SUMMARY OF STUDY DATA

All continuous variables will be summarised using the following descriptive statistics: n (non-missing sample size), mean, standard deviation, median, maximum and minimum. The frequency and percentages (based on the non-missing sample size) of observed levels will be reported for all categorical measures. In general, data listed will be sorted by medical center, treatment, and participant or by medical center and participant. Summary tables including treatment will be structured with either a column for each treatment in the order (OVH, EVH) or as rows for each treatment in the same order. Each table will be annotated with the total population size relevant to that table/treatment, including any missing observations.

6.1 Subject Disposition

Participant disposition will be summarized for all participants that signed the consent form and for the randomized population. The following data will be presented:

- The number of participants screened, eligible, consented, randomized, and expected to be randomized by medical center (TABLE 2). This table also provides the number of participants randomized to each group by center.
- The number of participants screened and randomized by month for each medical center (TABLE 3).
- A figure of participants randomized and expected by month (FIGURE 1).
- A listing that will include the reasons for exclusion of participants who discontinued from the study. These will include reasons for ineligibility (TABLE 4), non-enrollment (TABLE 5), and non-randomization (TABLE 6).
- Participant disposition by medical center for all participants (TABLE 7).

6.2 Demographics

Demographic characteristics at baseline will be summarized for all study participants. Demographic characteristics of all study participants will include age, gender, race/ethnicity, marital status, and education. The summary will include:

- The number and percentage of participants with each category of gender, race/ethnicity, marital status, and education (TABLE 8).
- The sample size, mean, median, SD, minimum and Maximum values for the following:
 - Age – calculated using the participant’s birth date (birth date on Form 01).

Estimates of the baseline demographic characteristics will be presented for all study participants. Tables summarizing the important background characteristics by medical center and treatment will be prepared and submitted to the Study Group to provide an idea of the population being studied, and based on this information, comparisons of the participant characteristics among the centers will be possible.

6.3 Baseline Variables

6.3.1 Seattle Angina Questionnaire

The sample size, mean, median, SD and minimum and maximum values for the 5 component scores including angina stability, angina frequency, physical limitation, treatment satisfaction, and quality of life will be reported for the baseline visit, overall by medical center and treatment (TABLE 9).

6.3.2 VR-12

The sample size, mean, median, SD, minimum, and maximum values for the PCS and MCS scores from the VR-12 will be presented for the baseline visit, overall by medical center and treatment (TABLE 10).

6.3.3 Conversion to Open Harvest Procedure

The conversion rate from EVH to OVH among randomized participants will be presented, overall and by medical center and harvester (TABLE 11), along with a list of reasons by center for the conversion (TABLE 12). The conversion rate, excluding conversions completed because the unanticipated graft required an additional vein will also be reported (TABLE 13).

6.3.4 Complexity of Coronary Artery Disease and Mortality and Morbidity Risks

The sample size, mean, median, SD, minimum, and maximum values for Syntax scores, indicating the complexity of coronary artery disease (CAD), will be presented, overall and by medical center, by MACE type, by age group, and by diabetes status as well as by treatment group (TABLES 14-17). Similar tables will be produced for the mortality and morbidity risk measures, VA Surgical Quality Improvement Program (VASQIP) and STS risk of mortality.

6.3.5 Bilateral Mammary Artery Grafting

The rate of bilateral mammary artery grafting among randomized participants will be presented, overall and by medical center (TABLE 18).

6.3.6 Leg Incision Healing and Severity of Incisional Leg Pain

The rate of leg incision infection and disturbance, along with severity of incisional leg pain (little or no impact, some impact, substantial impact, or severe impact) at discharge and 6-weeks will be assessed, overall and by medical center (TABLES 19-20).

6.4 Treatment Exposure

Treatment exposure is the vein harvesting technique to which study participants are randomized to, OVH vs. EVH. The number and percentages of participants randomized to either OVH or EVH will be reported.

- OVH – the traditional method of saphenectomy for CABG. It is performed under direct vision using a single long incision or, more commonly, multiple smaller incisions (referred to as “bridging” technique) along the course of the vein. This approach minimizes manipulation and direct trauma to the conduit but is associated with potential for discomfort and leg wound healing complications.
- EVH – is a minimally invasive procedure that was developed to eliminate the need for long incisions associated with OVH. EVH reduces the risk of wound infections and other leg wound complications but may be more traumatic to the conduit than OVH.

6.5 Study Endpoint

The rate of MACE and its components (all-cause mortality, nonfatal myocardial infarction, & repeat revascularization) will be reported, overall and by treatment (TABLE 21). Mean length of follow-up (in days) will also be reported by medical center and treatment (TABLE 22).

6.6 MACE by Harvester Experience

6.6.1 MACE by General Experience

The rate of MACE and its components (all-cause mortality, nonfatal myocardial infarction, & repeat revascularization) will be reported by harvesters' general experience: < 5 years, > 5 but < 10 years, and > 10 years. A separate table (similar to TABLE 21) will be provided for each level of experience.

6.6.2 MACE by EVH Experience

The rate of MACE and its components (all-cause mortality, nonfatal myocardial infarction, & repeat revascularization) will be reported by harvesters' EVH Experience: > 100 but < 500, > 500 but < 1,000, > 1,000 but < 2,000, and >2,000 endoscopic vein harvests completed. A separate table (similar to TABLE 21) will be provided for each level of experience.

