The other secondary outcome measures are MACE at one and three-year post surgery, leg wound healing complications and Quality of Life.

Two leading vendors (Maquet and Terumo) are currently marketing EVH device technologies for CABG. Device-related and procedural information will be collected during the study.

Subjects will receive concomitant optimal medical therapies (OMT) in both groups as recommended by the current 2011 American College of Cardiology/American Heart Association guidelines [Smith 2011]. OMT will include formal smoking cessation counseling and the administration of aspirin, beta blockers, angiotensin converting enzyme inhibitors, and lipid-lowering medications.

FIGURE 1. STUDY FLOW DIAGRAM

VI. Subject Population

All subjects who are candidates for CABG and who will undergo surgery at a VAMC with demonstrated expertise for both OVH and EVH and qualify to participate in CSP-sponsored research will be invited to participate in the REGROUP study.

A. Inclusion Criteria:

- Age 18 years or older
- Elective or Urgent CABG-only
- Median sternotomy approach
- At least one coronary bypass planned using saphenous vein graft for conduit
- Experienced EVH/OVH harvester and participating surgeon available for procedure

B. Exclusion Criteria:

- Combined valve procedure planned
- Moderate or severe valve disease (see definition of moderate/severe valve)
- Hemodynamically unstable or in cardiogenic shock
- Enrolled in another therapeutic or interventional study
- Off-pump CABG procedure planned
- Limited life expectancy < 1 year
- History of lower extremities venous stripping or ligation
- Inability to provide informed consent

C. Recruitment and Screening

We propose a prospective, multicenter, two-arm, randomized clinical trial (RCT). A block randomization technique will ensure equal distribution of subjects, within each harvester, within each site, in both arms of the trial. The randomization schema will be generated using SAS (SAS, Cary, NC).

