All participating centers must be able and willing to adhere to the study protocol. The minimum requirements for participating medical centers include:

- Site Principal Investigator: Each center must identify their site's principal surgeon investigator who enthusiastically supports the study and is willing to devote sufficient time and energy to ensure that the study's goals are met. For VA medical centers, the site surgeon investigator must have at least a 5/8th VA appointment for receiving VA research funds.
- EVH/OVH Harvester: Each center/study surgeon investigator must identify their site's harvester(s). The harvester(s) must have performed a minimum of 100 EVH procedures with a conversion rate to OVH < 5% to qualify for participation in the REGROUP trial. Each harvester must also demonstrate competency in OVH or the study surgeon investigator directly attending the case must perform the OVH in the same manner as provided during the course of usual care

absent a clinical trial. A subcommittee of the Executive Committee will convene and review each site's harvester qualifications and issue guidance/recommendations for sites as needed.

- Enrollment Volume: Each center must provide documentation that it will be able to recruit 24 subjects receiving a CABG-only procedure per year into the study who meet all inclusion/exclusion criteria. This total will be 72 subjects receiving CABG-only procedures over the three-year recruitment period.
- Administrative Support: Each center must provide assurance by the Chief of Surgery Service and/or the Chief of Staff that their site investigator will receive full administrative support.
- Multiple Participating Surgeons: At each center, there should be at least one (and preferably two or more) cardiothoracic surgery attending faculty team members participating that agree to randomize and operate on all consenting, eligible subjects with a planned CABG-only on-pump procedure using a median sternotomy incision. Although participating surgeons may enter/leave the study (after approval by the Chairman's office and Perry Point CSP Coordinating Center), the center must make every effort to recruit and to retain at least one qualified participating surgeon to enroll subjects in this study.

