2 STUDY OBJECTIVES AND ENDPOINTS

2.1 Study Objectives and Hypotheses

Primary Objectives:

Objective 1: To investigate the impact of SVG harvesting techniques – OVH vs. EVH on MACE, a composite end point of all-cause mortality, nonfatal myocardial infarction and repeat revascularization, over the active follow-up period of the study postoperatively.

Hypothesis 1: A significantly smaller proportion of CABG subjects with SVGs harvested by open technique will experience MACE post-surgery compared to CABG subjects with SVGs harvested by endoscopic technique during the active follow-up period.

Secondary Objectives:

Objective 2: To investigate the impact of SVG harvesting techniques – OVH vs. EVH on MACE, a composite endpoint of all-cause mortality, nonfatal myocardial infarction and repeat revascularization, at one and three-year postoperatively.

Hypothesis 2: One-year composite MACE rate will be 6 percentage points lower in the open harvesting group and three-year composite MACE rates will be at least 8-10 percentage points lower in the open vein harvesting group compared to the endoscopic vein harvesting group.

Objective 3: To investigate the impact of SVG harvesting techniques – OVH vs. EVH on MACE, a composite endpoint of all-cause mortality, nonfatal myocardial infarction and repeat revascularization, over the entire follow-up period (active and passive) of the study postoperatively.

Hypothesis 3: A significant smaller proportion of CABG subjects with SVGs harvested by open technique will experience MACE post-surgery compared to CABG subjects with SVGs harvested by endoscopic technique during the entire follow-up period.

Tertiary Objectives:

Objective 4: Investigate the impact of the two harvesting techniques - open vs. endoscopic - on clinical indicators of leg wound complications and subject satisfaction at six weeks post-surgery.

Hypothesis 4: Leg wound complications will be lower and satisfaction will be higher in the EVH group compared to OVH group.

Objective 5: Compare subject quality of life scores according to the SVG harvest technique at six weeks post-surgery.

Hypothesis 5: Subjects' quality of life scores will be higher in the EVH group compared to the OVH group.

Objective 6: Determine the role of vein harvester experience on clinical outcomes.

Exploratory Aim with no hypothesis specified.

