2.2.2 Secondary and Tertiary Outcome Measures

Secondary outcomes include MACE at one and three-year and over the entire follow-up period (active and passive) of the study postoperatively. Tertiary outcomes include leg wound complication and quality of life.

For hypothesis 2: MACE at one and three-year postoperatively.

For hypothesis 3: MACE over the entire follow-up period (active and passive) of the study postoperatively.

For hypothesis 4: Assessment of leg wound complications will be assessed at the time of discharge and at approximately six-week post-surgery during a clinic visit (this visit will take place between approximately 4 to 8 weeks post-surgery). Post-operative leg wound complication status (yes/no) will be determined based on these assessments.

For hypothesis 5: The Quality of Life (QoL) outcome measure will be the summary measures from the VR-12 instrument of health related quality of life as measured by the Physical Component Summary (PCS) and Mental Component Summary (MCS) and the Seattle Angina Questionnaire. QoL self-assessments will be completed at baseline, six weeks, and one year (by mail or telephone). Additionally, participants will be categorized as “improved”, “no change”, or “worsened” based on their baseline scores.

For hypothesis 6: Clinical measures include MACE.

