6.6.3 MACE by OVH Experience

The rate of MACE and its components (all-cause mortality, nonfatal myocardial infarction, & repeat revascularization) will be reported by harvesters' OVH Experience: < 50, > 50 but < 100, > 100 but < 500, > 500 but < 1,000, >1,000 but < 2,000, and >2,000 endoscopic vein harvests completed. A separate table (similar to TABLE 21) will be provided for each level of experience.

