For each scale of the SAQ (angina stability, angina frequency, physical limitation, treatment satisfaction, & quality of life), participants will be categorized as “improved”, “no change” and “worsened” at 6-weeks and 12 months compared to their baseline scores (TABLE 29). The proportion of participants in these three categories at each time point will be compared between the two groups using Pearson's chi-square test. The actual scores from these measures and that of the VR-12 MCS and PCS will be used to compare harvesting techniques using ANCOVA techniques, where the baseline (pre-surgery) scores will be used as a covariate (TABLE 30).

The hypotheses for the tertiary aims of this study are:

H4: Leg wound complications will be lower and satisfaction will be higher in the EVH group compared to OVH group.

H5: Subjects' quality of life scores will be higher in the EVH group compared to the OVH group.

H6: Exploratory Aim with no hypothesis specified.

The leg wound complication component of hypothesis H4 will be supported when the percent of participants experiencing leg wound complications randomized to EVH is lower than that of participants randomized to OVH with a significant *p*-value observed. Higher patient satisfaction in the EVH group vs. OVH group will be supported by a significant effect for treatment when entered into the ANCOVA model and a positive coefficient for EVH vs. OVH. The hypothesis H5 will be supported by a significant effect for treatment when entered into the ANCOVA model and a positive coefficient for EVH vs. OVH for the outcomes of SAQ quality of life scale, VR-12 PCS, and VR-12 MCS.

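### For Objective 6 the plan specifies no analysis of whether the EVH–OVH effect on MACE varies with harvester experience, and does not say whose experience counts when a different person performs OVH

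*SAP*

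**What the plan says.** SAP 2.1 lists "Objective 6: Determine the role of vein harvester experience on clinical outcomes" among the tertiary objectives. SAP 2.2.2 names the outcome: "For hypothesis 6: Clinical measures include MACE". SAP 7.3 repeats the objective, gives no method for it, and closes with "H6: Exploratory Aim with no hypothesis specified".

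The dedicated output is in SAP 6.6.1 (years of general experience, 3 levels), 6.6.2 (EVH count, 4 levels) and 6.6.3 (OVH count, 6 levels). For each: "A separate table (similar to TABLE 21) will be provided for each level of experience". The Table 21 shell has OVH, EVH and Total rows with N and %, for MACE and its three components.

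Experience appears in two other places. SAP 7.1, like Protocol XVII.D and Appendix D, gives it as an example of an adjustment covariate in the Cox model for time to MACE. Protocol Appendix D also puts it in the leg-wound logistic model. Both are main effects.

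On who operates, Protocol VI.C says: "A block randomization technique will ensure equal distribution of subjects, within each harvester, within each site, in both arms of the trial". Protocol XIV requires each harvester to be competent in OVH, "or the study surgeon investigator directly attending the case must perform the OVH". Appendix F (category B) likewise accepts a site whose harvester is experienced in EVH but not OVH, provided a designated OVH harvester is also available. Form 17 question 9 records which kind of harvester each one is.

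**The concern.** The protocol's background describes EVH as operator dependent, cites more vein injury with novice harvesters, and criticises two earlier sub-analyses for leaving out experience-related EVH variables. A reader will therefore want to know whether any EVH deficit shrinks as experience grows. That is a question about effect modification, and neither a main-effect covariate nor a set of separate tables estimates it.

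Thirteen tables read side by side invite conclusions from chance differences. The tables do not state a follow-up window. Active follow-up runs from a minimum of 1 year to about 4.5 years, so crude percentages at different levels may rest on different exposure.

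Where a second person performs OVH, blocking within the assigned harvester does not hold the operator constant. Technique and operator then differ together between arms. The SAP does not say whether an OVH patient at such a site is filed under the assigned harvester's experience or that of the person who did the harvest.

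**Working it through.** **Reproducing the plan's sizing.** Inputs are in Protocol XVII.B and SAP 3.6. For 9.5% v 15.5%, two-sided 0.05, 85% power, pooled variance:

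n = [1.960·√(2·0.125·0.875) + 1.036·√(0.095·0.905 + 0.155·0.845)]² / 0.06² ≈ 544.0, rounded up to **545 per group**. Then 1,090 / 0.95 = 1,148, stated as about 1,150.

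The second statement (MACE-free 83.5% v 91.5%, 532 per group) implies a hazard ratio of ln 0.915 / ln 0.835 = 0.493 and 532 × (0.165 + 0.085) = 133 events. By Freedman's formula, √133 × (1 − 0.493)/(1 + 0.493) − 1.96 = 1.96, which is **97.5% power**, as stated. With 575 per group the events are 575 × 0.25 ≈ 144. I use 133 to 144 below.

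**What the separate tables can carry.** The documents give no distribution of experience, so an even spread of 1,150 patients is an assumption. The 95% half-width for the risk difference is 1.96·√[(0.165·0.835 + 0.085·0.915)/n per arm].

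| Levels | n per arm per table | Expected events EVH / OVH | 95% half-width |
|---|---|---|---|
| 3 | 192 | 32 / 16 | 6.6 points |
| 4 | 144 | 24 / 12 | 7.6 points |
| 6 | 96 | 16 / 8 | 9.3 points |

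The assumed difference is 8 points. An uneven spread makes the sparse levels worse. SAP Table 11 has 32 harvester rows at 16 centres: about 1,150 / 32 = 36 patients per harvester and 32 / 6 ≈ 5 harvesters per OVH level. Experience level is therefore closely tied to site.

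**What one interaction term can carry.** Simplify experience to two groups, with a share q of the D events in one group. The standard error of the log ratio of hazard ratios is √[4/(Dq) + 4/(D(1−q))]. The ratio detectable with 80% power is exp[(1.960 + 0.842) × SE].

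| Split (assumed) | SE, D = 133 / 144 | Ratio for 80% power | Power if ratio is 2.0 | Power if ratio is 1.5 |
|---|---|---|---|---|
| 50:50 | 0.347 / 0.333 | 2.64 / 2.54 | 52% / 55% | 21% / 23% |
| 25:75 | 0.400 / 0.385 | 3.07 / 2.94 | 41% / 44% | 17% / 18% |

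These figures are somewhat favourable: they take events as evenly split between arms and ignore variation in effect between harvesters.

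**Who is classified.** Randomization is within the assigned harvester (Protocol IX.B, SAP 3.4), and Form 01 question 18 records that harvester's ID. Form 05 question 52 records only a profession code for the person who harvested. Classification by assigned harvester therefore uses a variable fixed before allocation and available for every patient. Classification by actual operator is not directly supported by these forms and, where operators differ by arm, would sort patients by something that depends on allocation.

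**The case against.** Objective 6 is tertiary and exploratory, and no decision depends on it. Descriptive tables are a legitimate choice there, and an underpowered interaction p-value can be over-read as easily as a table. The protocol also limits gross inexperience by requiring at least 100 EVH cases and low conversion rates, and it reports that a sensitivity analysis in ROOBY found no differential effect by centre EVH volume. All of this stands. It makes the point minor, and it argues for an estimate with an interval rather than a bare test.

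Four stronger readings are tempting, but the documents do not support them.

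- A reader might infer that experience is handled by crude tables alone. The Cox model may include it as a covariate, which can estimate its association with MACE. What is missing is effect modification.
- A reader might infer that different people do perform EVH and OVH at some sites. The rules permit this, but nothing shows that any of the 16 sites qualified that way.
- A reader might infer that the trial cannot answer the question. Blocking within harvester supports a comparison of arms at each level, Table 21 already splits by arm, and where one person does both techniques the operator is held constant. The analysis is unspecified, not impossible.
- A reader might take SAP 6.6.3, which ends its list with ">2,000 endoscopic vein harvests completed", to define OVH experience by endoscopic counts. Its heading says OVH and its bins match Form 17 question 7, which counts open harvests, so this is a copying slip.

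**Conclusion.** The point holds as a minor, inexpensive improvement. The SAP specifies no analysis that estimates whether the EVH–OVH effect on MACE depends on harvester experience, and it leaves classification open where operators differ. The dedicated output is 13 uncompared tables; under an even spread, their half-widths of about 7 to 9 points are close to or larger than the 8-point effect assumed for the whole trial.

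One model would use the same data better but would not make the question well powered. With 133 to 144 events it reliably detects only a ratio of hazard ratios of about 2.5 to 2.6 at a 50:50 split, or 2.9 to 3.1 at 25:75. The splits, the even spread and the two-group simplification are assumptions. Level-specific hazard ratios would be randomised comparisons. The contrast between levels would remain observational, because harvesters are not randomised to experience. The primary analysis is unaffected.

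**What to change.** In SAP 7.3, make the basis for Objective 6 one exploratory Cox model of time to MACE over active follow-up. Its terms are treatment, the ordered EVH-count category (Form 17 question 5) of the harvester assigned on Form 01, and their interaction, with allowance for clustering by harvester. State that the harvester is the one under whom the patient was randomized, whoever performs the harvest.

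Report level-specific hazard ratios with 95% confidence intervals and the interaction estimate in one display, labelled exploratory and low-powered. Keep the tables in 6.6.1 to 6.6.3 as descriptive support and state their follow-up window.

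Add a sensitivity analysis restricted to harvesters recorded on Form 17 question 9 as experienced in both techniques. Correct 6.6.3 to open harvests. While editing, assign the boundary values that the bins omit, such as exactly 5 years or exactly 500 cases.

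The cost is SAP wording, one model and one sensitivity run. Forms 01 and 17 hold the experience data, so nothing new is collected. The downside is low interaction power: a null interaction must not be read as evidence that experience is irrelevant.
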